Analysis of secondary endpoints: The secondary outcome will compare treatment groups on the change in depression symptoms from baseline to day 31 using weekly scores from the MADRS and HDRS. A similar mixed-effects model used for the primary endpoint will be applied. The trajectories of MADRS and HDRS mean scores will be compared between the two groups in the mixed model with statistical significance determined by the p-value for the treatment group by time interaction term. If the groups differ significantly on the MADRS scores, the proportion of responders (i.e., >50% or greater reduction from

baseline to day 31) will be statistically with a 2x2 chi-squared test. The MADRS depression assessment includes one item that assesses suicidal thoughts. Mean scores and standard deviations on this item will be calculated for the K+Buprenorphine and K+Placebo groups, and effect sizes will be calculated using Glass's formula.

Analysis of safety endpoints: Frequencies of side effects, adverse events, and serious adverse events observed during the active treatment phase will be summarized by group, and the most commonly reported adverse events will be tabulated. Changes in suicidality and withdrawal symptoms during the 2-week post intervention phase (days 38 and 45) will be described with means, standard deviations, and ranges for the SSI and MADRS, as well as for clinician and patient ratings of withdrawal (COWS and SOWS). These measures will be compared across groups using independent measures t- tests. No type 1 error correction is planned for safety analyses.

Evaluation of treatment blind: Two-weeks post-intervention (day 45), patients will be asked to endorse one of the following: I think I was taking active medication; I think I was taking placebo; I am unsure if I was taking an active medication or a placebo. Frequency counts and percentages will describe the correct and incorrect guesses.

Missing data: For both primary and secondary endpoints, the mixed-effects models implicitly assume data missing at random. Sensitivity analyses will only be conducted if necessary (e.g., if the missingness is non-ignorable due to high frequency of missingness or if data are not missing at random).

Sample size justification: The only RCT evaluating buprenorphine for reducing suicidality was that of Yovell and colleagues. They calculated that a sample of 75 participants with a 2:1 randomization ratio would provide 80% power at a 5% significance level to detect a 6.3-point difference between groups in scores on the Scale for Suicide Ideation, assuming a standard deviation of 9.0. They observed that patients in the buprenorphine group had a greater reduction in Suicide Ideation Scale score than patients in the placebo group, (mean difference= -4.3, 95% CI=-8.5, -0.2; p=0.04) at week 2 and at the end of week 4 (mean difference=-7.1, 95% CI=-12.0, -2.3; p=0.004). Sensitivity analysis revealed similar results (mean difference=-5.7, 95% CI=-10.1, 21.4; p=0.01).

Based on effect sizes observed by Yovell et al on the same endpoint measure of SSI, the a priori power calculation for the current study indicated n=60 patients would have 80% power to detect medium effect sizes of .35 or greater on the primary outcome of the group differences in SSI. (We did not power the study to test the differences between groups on secondary measures).

10. References:

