7.3. Lost to Follow-up

A participant will be considered lost to follow-up if he or she fails to return for one scheduled visit and is unable to be contacted by the study staff.

We will take the following actions if a participant fails to return for a required study visit:

- We will attempt to contact the participant and reschedule the missed visit within 24 hours and counsel the participant on the importance of maintaining the assigned visit schedule and ascertain if the participant wishes to and/or should continue in the study.
- Before a participant is deemed lost to follow-up, the investigator or his designee will make every effort to regain contact with the participant (where possible, 3 telephone calls and, if necessary, a certified letter to the participant's last known mailing address or local equivalent methods). We will record these contact attempts in the participant's designated REDCap e-CRF.
- Should the participant continue to be unreachable, he or she will be considered to have withdrawn from the study with the primary reason of loss to follow-up.

8. Study Assessments and Procedures:

8.1. Efficacy Assessments:

Screening process:

Participants will be recruited through the Stanford Depression Research Clinic online recruitment pipeline (online portal for referrals). Potential participants will be prescreened through their medical records. Participants whose initial prescreening is consistent with study eligibility will then be invited to consent to and participate in screening with a study team member (over zoom) for further assessment of eligibility. In-depth screening will include demographics information; psychiatric and medical history; current and past medications with adequacy of trials assessed by the Massachusetts General Hospital (MGH) Antidepressant Treatment Response Questionnaire (ATRQ); psychiatric diagnoses via the Overview/History section of the Structured Clinical Interview for DSM-5 (SCID) and the Mini-International Neuropsychiatric Interview for DSM-5 (MINI); borderline personality disorder screener and diagnostic module from SCID for DSM-5 (if a participant meets the screening threshold on the self-reported pre-screening questions); suicidal ideations will be measured by the Scale for Suicidal ideation (SSI); depression assessment with the Hamilton Depression Rating Scale (17-item), and the Montgomery-Åsberg Depression Rating Scale (MADRS).

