treatment phase. Although ITT estimates theoretically have less bias, the mITT is a conservative decision for the current design in which all patients will first receive ketamine. Including patients who only received ketamine and completed no assessments past the ketamine phase (days 1 to 3) would provide no information regarding response to follow-on buprenorphine or placebo. Moreover, given the known antidepressant effect of ketamine on suicide, their inclusion would likely underestimate the projected means at time points during the post-ketamine evaluation of 4 weeks of follow-on buprenorphine vs placebo.

Repeated measurements of the SSI will be compared across treatment groups using a linear mixed-effects model. The mixed model makes use of all available SSI scores across the study timepoints to estimate group differences in means. The model will include fixed effects of treatment group, time, time by treatment group interaction, and a random effect of participant intercept. An unstructured covariance matrix, or a first order auto-regressive structure, will be used based on relative model fit according to the information criterion index. This model parameterization is suited for testing of between-group differences over repeated measurements, consistent with the primary study hypothesis. The SPSS syntax is:

MIXED SSI with time treatment

/Criteria=CIN(95) MXITER(100) MXSTEP(10) SCORING(1)

SINGULAR (0.0000000001) HCONVERGE(0, ABSOLUTE) LCONVERGE(0, ABSOLUTE),
PCONVERGE(0.00000001, ABSOLUTE)

/FIXED time time*treatment | SSTYPE(3)

/METHOD=ML

/RANDOM=INTERCEPT time | PARTICIPANT COVTYPE(UN).

The result of the hypothesis test for efficacy of Ketamine followed by Buprenorphine will be determined by the statistical significance of the treatment by time interaction (two-sided $\alpha=.05$). Only if group differences are deemed statistically significant on the prespecified primary outcome, a supplemental analysis of clinical significance will be conducted by calculating the proportion of responders, defined as a 50% or greater reduction in SSI suicidality ratings from baseline to day 31, in each of the two treatment groups. These proportions will be compared with a 2x2 chi-squared test.

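### Section 7.3 makes loss to follow-up final after one missed visit and failed contact, so a participant who reappears before Day 31 can lose the primary SSI value

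*Combined protocol and SAP*

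**What the plan says.** Section 7.3 (Lost to Follow-up) sets the trigger: a participant "will be considered lost to follow-up if he or she fails to return for one scheduled visit and is unable to be contacted". The section then lists what staff do. They are to "attempt to contact the participant and reschedule the missed visit within 24 hours". The next step is stated as a precondition: "Before a participant is deemed lost to follow-up, the investigator or his designee will make every effort to regain contact with the participant", which means, where possible, "3 telephone calls and, if necessary, a certified letter". The last step reads "Should the participant continue to be unreachable, he or she will be considered to have withdrawn from the study", with loss to follow-up recorded as the primary reason.

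No minimum or maximum time is set for these steps. The section does not say what happens if the participant turns up later, and it plans no further attempt at the Day 31 rating.

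Related text elsewhere:
- Section 1.5 (Schedule of Activities): SSI is rated on Days 10, 17, 24, 31, 38 and 45, each within plus or minus 2 days. The Day 5 phone contact includes MADRS and C-SSRS but not SSI.
- Section 6: study drug starts after the Day 3 ratings.
- Section 7.1: missed visits may lead to removal, and withdrawn participants are replaced only if they leave before the first treatment day (Visit 3) is complete.
- Section 8.1: screening, which includes the SSI, is done by video.
- Section 9: the primary endpoint is SSI reduction from baseline to Day 31. The mITT set requires at least one SSI in the active treatment phase. On the analysis, "The mixed model makes use of all available SSI scores across the study timepoints". The model assumes data missing at random, and sensitivity analyses are done only if judged necessary.

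**The concern.** The primary model can handle a participant who misses a week and comes back. The follow-up rule has no matching provision. Once the contact steps have failed, the participant's status is withdrawn from the study, even with most of the randomized phase still ahead. Because the steps have no minimum length, they could be exhausted within days of a missed Day 10 or Day 17 visit.

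Two things are at stake. The first is the Day 31 SSI of a participant who reappears. The second is membership of the analysis set: someone closed out at Day 10 has SSI ratings only from before study drug, so a randomized participant drops out of the primary analysis altogether. In a suicidal population, being out of reach may also be related to current suicidality. If so, the missing values may strain the missing-at-random assumption on which the model rests.

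**Working it through.** **1. Visits still ahead.** From section 1.5, after a missed Day 10 visit five remain (Days 17, 24, 31, 38, 45). After a missed Day 17 visit four remain, and after a missed Day 24 visit three.

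**2. What each early close-out leaves for the analysis.**
- Lost at Day 10: SSI exists for Day 1 and Day 3 only. Section 6 starts study drug after the Day 3 ratings, section 9 counts Days 1 to 3 as the ketamine phase, and Day 5 has no SSI. There is no active-phase SSI, so the participant is outside the mITT set.
- Lost at Day 17: the Day 10 score remains. The participant stays in the mITT set without a Day 31 value.
- Lost at Day 24: the Day 10 and Day 17 scores remain, again without Day 31.

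**3. Size.** The documents give no attrition rate and no attrition allowance, so there is no figure of the plan's own to reproduce here. Assume a chance p, constant and independent across Days 10, 17, 24 and 31, that a visit is missed and the participant cannot be contacted.
- If every such gap is final: share without Day 31 SSI = 1 − (1 − p)^4.
- If every such gap is temporary and returning participants are assessed: share = p.
- If only a fraction r of those closed out before Day 31 would have reappeared: avoidable loss = r × {[1 − (1 − p)^4] − p}.

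| Assumed p | All gaps final | All gaps temporary | Avoidable, r = 1 | Avoidable, r = 0.5 | Avoidable, r = 0.25 |
|---|---|---|---|---|---|
| 1% | 1 − 0.99^4 = 3.9% (2.4 of 60) | 1% (0.6) | 2.9 points (1.8) | 1.5 points (0.9) | 0.7 points (0.4) |
| 2% | 1 − 0.98^4 = 7.8% (4.7 of 60) | 2% (1.2) | 5.8 points (3.5) | 2.9 points (1.7) | 1.4 points (0.9) |
| 5% | 1 − 0.95^4 = 18.5% (11.1 of 60) | 5% (3.0) | 13.5 points (8.1) | 6.8 points (4.1) | 3.4 points (2.0) |

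Figures in brackets are participants out of 60. The r = 1 column is the upper bound on what a changed rule could recover. Both p and r are assumptions.

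**4. Loss from the mITT set at Day 10.** If every gap is final, the expected number is 60p: 0.6 participants at p = 1%, 1.2 at 2% and 3.0 at 5%.

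**5. What the model recovers.** Participants lost at Day 17 or Day 24 still inform the fitted trajectories through their earlier on-drug scores, so the information lost is less than the count of missing Day 31 values suggests. Those lost at Day 10 contribute nothing to the mITT analysis.

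**The case against.** The strongest defence is that section 7.3 is more careful than its first sentence. A participant who misses a visit but can be reached is rescheduled, so ordinary gaps stay temporary. The withdrawn status applies only to someone who remains unreachable after every attempt, and nothing in the text bars that person from returning. This stands. A reader might infer that one missed visit automatically ends follow-up; the documents do not support that. Nor do they say that the loss is permanent: that is an inference from the withdrawn status and the silence on re-entry.

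The second objection also stands. Someone who never becomes reachable has no Day 31 SSI under any definition, so the rule can cost data only from those who reappear. It would therefore be wrong to charge all loss to follow-up to this rule, for example by taking the power of a completer t-test at a reduced sample size as its effect. That would also ignore the partial data used by the mixed model.

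Third, a reader might infer that those lost are the most unwell and that missing at random is violated. The documents show neither. Missing at random permits dependence on SSI scores already observed, and outcome-related absence could arise under any follow-up rule. Only the possibility remains.

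Finally, video rating cannot help while a participant is unreachable. It helps a participant who can be reached but cannot attend.

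None of this answers the remaining gap: final status can be assigned weeks before the primary time point, after steps of no stated length, with no plan to seek the primary outcome afterwards.

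**Conclusion.** The point holds in a limited form. After one missed visit and failed contact attempts, section 7.3 treats the participant as withdrawn, sets no minimum duration for those attempts, and plans no later attempt at the Day 31 SSI. The avoidable harm falls on participants who are unreachable for a time and reappear before Day 31. For those closed out at Day 10 it includes exclusion from the mITT set.

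The size cannot be known from the documents. Under the assumed rates of 2% and 5% per visit, at most 5.8 and 13.5 percentage points of Day 31 values (3.5 and 8.1 of 60 participants) could be saved, and proportionately fewer if only some participants return. The mixed model softens the loss where earlier on-drug scores exist. A strain on the missing-at-random assumption is possible but not shown. The change is worth making because it is cheap and protects the primary endpoint in a trial of 60 with no stated allowance for attrition.

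**What to change.** In section 7.3:
- Assign final lost-to-follow-up status only when the Day 31 window, preferably the Day 45 window, has closed without contact.
- Until then, repeat the contact attempts at each scheduled visit.
- Collect the SSI, MADRS and C-SSRS at the remaining visits from anyone who reappears and has not withdrawn consent, whether or not study drug continues.
- When a reachable participant cannot attend, allow video rating within the visit window and record it as remote.
- Do not record a participant as withdrawn from the study solely because he or she is unreachable.

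The provisions for withdrawal by the investigator in sections 7.1 and 7.2 stay as they are; this change concerns only participants who cannot be reached.

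The cost is protocol wording, a few more calls, and some ratings made by video instead of on site.

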Participants will also be asked specifically about any significant neurologic disease, including dementia, Parkinson's or Huntington's disease, brain tumor, seizure disorder, subdural hematoma, multiple sclerosis, or history of significant head trauma; history of dementia or cognitive impairment; and whether they are receiving or planning to receive any other investigational treatments during this study. Screening will be performed by a consistent group of qualified study staff who have been trained and certified by the lab's Psychological Director to ensure fidelity to assessment procedures.

Screening must be completed within 2 weeks of formal study enrollment and baseline assessment, otherwise screening will need to be repeated prior to moving forward with enrollment and baseline assessment.

Efficacy assessments related to primary and secondary outcomes:

We will use the following clinical scales to quantify suicidal ideation: Scale for Suicide Ideation (SSI), Columbia-Suicide Severity Rating Scale (C-SSRS). General mood and anxiety will be quantified using the Montgomery Åsberg Depression Rating Scale (MADRS), and 21 items Hamilton Depression Scale (HAM-D-21).

8.2. Safety and Other Assessments:

All patients will undergo a clinical study visit with the study psychiatrist (or their designee) as part of the assessment for suitability in the study. This visit will include assessment of current psychiatric symptoms, psychiatric history (including past diagnoses, hospitalization, suicide attempts, past medication trials), current medical concerns (if any), past medical history, current medications, allergies, family psychiatric history, and social history. A mental status exam will be performed. Vital signs and certain studies (e.g., EKG, basic labs) will be obtained. Follow up clinical study visits will be performed.

8.3. Adverse Events and Serious Adverse Events:

8.3.1. Definition of Adverse Events:

An adverse event (AE) is any untoward, undesired, or unplanned event in the form of signs, symptoms, disease, or laboratory or physiological observations occurring in a person who has received study interventions. The event need not be causally related to the ketamine infusion or buprenorphine/placebo treatment in order to be considered an AE.

An AE includes, but is not limited to:

- Any adverse finding including a sign, symptom, abnormal assessment (laboratory test value, vital signs, electrocardiogram finding, etc.), or any combination of these.

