- Any clinically significant worsening of a pre-existing condition;
- An AE that has been associated with a preexisting condition is a clinical condition (including a condition being treated) that is diagnosed before an informed consent form is signed and is documented as part of the subject's medical history.

The questions concerning whether the condition existed before the start of the active phase of the study and whether it has increased in severity and/or frequency will be used to determine whether an event is an intervention-emergent AE (IEAE).

An AE is considered to be intervention-emergent if [1] it was not present when the active phase of the study began and is not a chronic condition that is part of the subject's medical history, or [2] it was present at the start of the active phase of the study or as part of the subject's medical history, but the severity or frequency increased during the active phase.

For this study, the treatment follow-up period for adverse events is defined as 30 days following the last study visit.

Follow up will be documented in the subject's study file.

8.3.2. Definition of Serious Adverse Events:

A Serious Adverse Event (SAE) is defined as an AE that:

- Results in death
- Is life threatening (see below)
- Requires inpatient hospitalization or prolongation of an existing hospitalization (see below)
- Results in a substantial disruption of a person's ability to conduct normal life functions, i.e., the adverse event resulted in a significant, persistent or permanent change, impairment, damage or disruption in the patient's body function/structure, physical activities and/or quality of life
- Necessitates medical or surgical intervention to preclude such impairment
- Results in a congenital anomaly or birth defect

Additionally, important medical events that may not result in death, be life-threatening, or require hospitalization, may be considered SAEs, based upon appropriate medical judgment.

Life threatening refers to immediate risk of death as the event occurred or other medical intervention might have resulted in the death per the reporter. A life-threatening event does not include an event that,

had it occurred in a more severe form, might have caused death, but as it actually occurred, did not create an immediate risk of death.

Hospitalization is to be considered only as an admission. Hospitalization constitutes an AE to be classified as serious.

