An AE or SAE can occur from the time that the subject signs the informed consent form to 7 and 30 days, respectively, from the subject's last study visit regardless of relationship to the protocol. All AEs and SAEs will be recorded on the subject-specific and study wide eCRFs, which will be provided to the DSMB on a quarterly basis. The DSMB will instruct the Principal Investigator to follow all AEs, SAEs, and other reportable events until the event has subsided or values have returned to baseline, or in case of permanent impairment, until the condition stabilizes.

In addition to the information obtained from those sources, the subject will be asked the following nonspecific question: "How have you been feeling since your last visit?" Signs and symptoms will be recorded using standard medical terminology.

The following AE information will be included (when applicable): the specific condition or event and direction of change; whether the condition was preexisting (i.e., an acute condition present at the start of the study or history of a chronic condition) and, if so, whether it has worsened (e.g., in severity and/or frequency); the dates and times of occurrence; severity; causal relationship to the study interventions; action taken; and outcome.

8.3.6. Serious Adverse Event Reporting:

The PI or his designee will immediately report to the sponsor any serious adverse event (SAE), whether or not considered study intervention related, including those listed in the protocol or investigator brochure and must include an assessment of whether there is a reasonable possibility that the study intervention caused the event. Study endpoints that are serious SAEs (e.g., all-cause mortality) must be reported in accordance with the protocol unless there is evidence suggesting a causal relationship between the study intervention and the event (e.g., death from anaphylaxis). In that case, the investigator will immediately report the event to the sponsor.

All SAEs will be followed until satisfactory resolution or until the site investigator deems the event to be chronic or the participant is stable. Other supporting documentation of the event may be requested by the study sponsor and should be provided as soon as possible.

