In case of SAEs, the study investigator will complete an Unanticipated Serious Adverse Event Form and submit to the study sponsor and to the reviewing Institutional Review Board (IRB) as soon as possible, but in no event later than 10 business days after the investigator first learns of the effect. The study sponsor will conduct an evaluation of an unanticipated adverse event and will report the results of such evaluation to the Food and Drug Administration (FDA) and to all reviewing IRBs and participating investigators within 10 business days after the sponsor first receives notice of the effect. Thereafter, the sponsor will submit such additional reports concerning the event as FDA requests. The Investigator will provide all relevant documentation pertaining to an SAE (e.g., additional laboratory tests, consultation reports, discharge summaries, postmortem reports, etc.) to the DSMB in a timely manner. Reports relative to the subject's subsequent course will be submitted to the DSMB until the event has subsided or, in case of permanent impairment, until the condition stabilizes.

Other reportable information, while not meeting the definition of an SAE, is reportable to the DSMB with the timeliness of an SAE.

This includes:

- Seizure
- Pregnancy occurring during the study period in which the subject was exposed to study intervention;
- Overdose (e.g., a dose higher than that prescribed by a healthcare professional for clinical reasons) with or without AEs;
- Abuse (e.g., use for non-clinical reasons) with or without an AE;
- Inadvertent or accidental exposure with or without an AE;

Designated study staff will be responsible for ensuring that unanticipated problems are reported to the IRB in compliance with their requirements for reporting serious and unexpected adverse events. Reporting will be conducted in compliance with guidelines specified by the Stanford University Research Compliance Office.

8.3.7. Reporting Events to Patients:

At enrollment, participants will be asked whether or not they would like to be informed about study outcomes. We will compile a list of those participants who would like to know about outcomes, and following study completion they will be individually emailed a copy of the study's primary outcome paper using individual, encrypted email.

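### The endpoint carve-out conflicts with immediate SAE reporting, non-serious suicidal behaviour is not listed for prompt reporting, and C-SSRS behaviour has no by-arm summary through Day 45

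*Combined protocol and SAP*

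**What the plan says.** **Reporting of SAEs (Section 8.3.6).** The general rule is: "The PI or his designee will immediately report to the sponsor any serious adverse event (SAE), whether or not considered study intervention related". The next sentence reads: "Study endpoints that are serious SAEs (e.g., all-cause mortality) must be reported in accordance with the protocol unless there is evidence suggesting a causal relationship". For a suspected causal link with the intervention it then adds: "In that case, the investigator will immediately report the event to the sponsor".

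**What counts as serious (Section 8.3.2).** Death, a life-threatening event, inpatient hospitalisation, and an event needing medical or surgical intervention to prevent lasting impairment all qualify. On hospitalisation the section says: "Hospitalization is to be considered only as an admission". Other important medical events may be classed as serious on medical judgement, and any doubtful case is to be treated as an SAE.

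**Prompt reporting of other events (Section 8.3.6).** "Other reportable information, while not meeting the definition of an SAE, is reportable to the DSMB with the timeliness of an SAE". The list has five items: seizure, pregnancy, overdose, abuse, and inadvertent or accidental exposure.

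**Safety analysis (Section 9, Analysis of safety endpoints).** "Frequencies of side effects, adverse events, and serious adverse events observed during the active treatment phase will be summarized by group". For Days 38 and 45, SSI, MADRS and the two withdrawal scales are described and compared between groups by t-test.

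**C-SSRS.** The Schedule of Activities (Section 1.5) has it at every contact from screening to Day 45, including the Day 5 phone call. Section 8.1 names it, with the SSI, as a scale for suicidal ideation. Section 9 does not mention it.

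**The concern.** Suicidality is both the outcome and the main hazard in this population. Three features of the plan fit that poorly.

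First, two adjacent sentences give different instructions for a death judged unrelated: the general rule says report at once, and the exception names all-cause mortality as its example. Staff who took that example at face value could treat a suicide as an endpoint event. Under the causality scale in Section 8.3.3.2, an event most likely explained by the participant's clinical state is graded probably not related, so the causality clause might not restore immediate reporting.

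Second, the list of events sent promptly to the DSMB leaves out suicidal behaviour that falls short of the SAE definition.

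Third, the C-SSRS has no planned analysis. The report could show lower SSI scores without showing, by arm, how many participants had a suicidal behaviour, particularly after study drug stops. Section 2.3.2 names reduced suicidal ideation and behaviour as a possible gain.

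**Working it through.** The plan has no figure to reproduce here. The check sets the sections side by side and uses simple counts.

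**1. Does the exception apply to any event in this trial?**
- Endpoints in Sections 1.3 and 3: SSI change (primary), MADRS and HAMD change (secondary), and drug and metabolite levels, prolactin and pupillometry (other).
- None is a death or a suicidal event, and a change in a score is not itself an SAE. Read strictly, the exception covers nothing.
- Its mortality example still conflicts with the general rule, and the protocol contains no separate rule for reporting endpoint events.
- If a death were wrongly handled under it, two limits remain: any SAE goes to the IRB within 10 business days regardless of cause (Section 8.3.2), and the SAE form goes to the sponsor and IRB as soon as possible, at the latest within 10 business days (Section 8.3.6).
- Worst case on the misreading: 10 × 7/5 = 14 calendar days instead of immediately.

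**2. Which suicidal behaviour lacks a prompt route?**

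| Behaviour | Route |
|---|---|
| Fatal, life-threatening, or leading to admission | SAE |
| Needing intervention to prevent lasting impairment | SAE |
| Other important medical event | SAE on judgement |
| Seriousness in doubt | Treated as SAE |
| Overdose, with or without an AE | On the prompt list |
| None of these, e.g. an interrupted or aborted attempt | Not on the list |

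Only the last row is uncovered. Such an event reaches the DSMB through the quarterly forms and the IRB through the annual report (Section 8.3.5).

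**3. What is summarised by arm, and when?**
- C-SSRS time points: Screen, Baseline, Days 1, 3, 5, 10, 17, 24, 31, 38, 45 = 11.
- Section 6 starts study drug after the Day 3 ratings, so four time points (Screen, Baseline, Days 1 and 3) come before the first randomised dose. 11 − 4 = 7 follow it: Days 5, 10, 17, 24, 31, 38 and 45.
- Two of the seven, Days 38 and 45, come after drug is stopped. Section 6 puts the end of the active treatment phase at that stop, which the schedule places at Day 31.

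| Period | AEs and SAEs by arm | Suicidality scores by arm | C-SSRS by arm |
|---|---|---|---|
| First dose to Day 31 | Yes | SSI, MADRS (efficacy models) | None |
| Day 31 to Day 45 | No | SSI, MADRS (described, t-tests) | None |

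The second row spans 45 − 31 = 14 days. This is the period in which the protocol (Section 1.3, Description of Study Intervention) intends to look for discontinuation symptoms and recurrent suicidal ideation. Adverse events are reviewed at Days 38 and 45, so the data will exist. Mean scores do not show how many participants had a suicidal behaviour.

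**The case against.** The case on the other side is substantial. The exception is limited to study endpoints and none is a death, so the general rule governs. Serious suicidal behaviour is already an SAE, and treating doubtful cases as SAEs is mandatory. Overdose is on the list. Staff must report unexpected AEs to the principal investigator at once (Section 8.3.5), AEs are monitored continuously with DSMB involvement (Section 8.3.7), and exclusion criterion 11 removes people judged at significant risk of suicidal behaviour. All of this stands, and it rules out three stronger readings that a reader might infer.

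- *A death loses immediate reporting.* Not on the text as written. This happens only if the mortality example is misread, and the 10-business-day limit then still applies.
- *Suicidal behaviour is in no planned safety summary.* Too broad. During active treatment, an attempt recorded as an AE or SAE is counted in the by-group frequencies, and SSI and MADRS are compared afterwards.
- *Suicidal behaviour is handled more slowly than an accidental exposure, by up to a quarter.* Not established. Listed events follow SAE timeliness, but the DSMB's review of SAEs is also quarterly, and the only other DSMB timing for SAEs is documentation in a timely manner, with no number of days.

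The objection does not explain why an inapplicable, conflicting sentence should stay. Nor does it supply a by-arm account of suicidal behaviour after Day 31, or any use of the C-SSRS in Section 9.

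**Conclusion.** The point holds in a narrow form and is a low-cost improvement. It does not show that the trial's safety reporting fails.

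- The exception in Section 8.3.6 contradicts the sentence before it and has no proper use here. The exposure is at most about 14 calendar days, and only on a misreading.
- Suicidal behaviour that is neither an SAE nor an overdose is missing from the prompt list. No number of days gained can be claimed from adding it, because the DSMB has no numeric clock for SAEs.
- The C-SSRS has seven time points after the first randomised dose and no planned analysis. For the 14 days after drug is stopped, suicidal behaviour appears in no by-arm safety summary.

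This rests on two assumptions: that the active treatment phase ends when study drug stops at Day 31, as Section 6 indicates, and that the C-SSRS form in use records behaviour as well as ideation, which the protocol does not spell out.

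**What to change.** 1. **Section 8.3.6:** delete the sentence on endpoint SAEs and the one after it, so that the immediate-reporting rule covers every SAE, including every death.
2. **Section 8.3.6, list of other reportable events:** add C-SSRS suicidal behaviour that does not meet SAE criteria.
3. **Section 9, Analysis of safety endpoints:** extend the by-arm AE and SAE summary through Day 45. Add a by-arm table of the number of participants with any C-SSRS suicidal behaviour, and of the worst ideation category, after the first randomised dose through Day 45. Show the Day 3 pre-dose rating as the reference.

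The table should be descriptive, without a test. The changes need no new assessment and touch no dose, stopping rule or clinical threshold. The cost is two sentences removed, one list item, one extended summary and one table, plus a few more prompt notices to the DSMB.
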